4.2.2 Exploratory Endpoints

Exploratory endpoints are related to efficacy and success of blinding:

- Response on ear pain scores at 10, 20, 30, and 60 minutes post dose using the VAS and the NRS-11
- Pain Intensity Difference (PID) from Baseline of the VAS and the NRS-11 at 10, 20, 30, and 60 minutes post dose
- Sum Pain Intensity Difference (SPID) of the VAS and the NRS-11 over 60 minutes post dose
- Time to ear pain relief in affected ear(s), recorded as change from moderate/severe pain to mild or no pain using the VAS and the NRS-11
- PGIC measured at 10, 20, 30, and 60 minutes post dose
- CGI-I scale measured at 60 minutes post dose
- Presence of AOM symptoms
- Response on the Blinding Index at 60 minutes post dose
- Response on Device Experience Questionnaire Subject
- Response on Device Experience Questionnaire Study Staff Administering Treatment

5. SAMPLE SIZE

Approximately 24 Study Participants will be randomized. Additional Study Participants will be randomized for Study Participants who discontinue the study prematurely.

6. TREATMENT ASSIGNMENT, BLINDING, AND UNBLINDING

6.1 Treatment Assignment

Following Screening, but before any treatment-related procedures, eligible Study Participants will be randomly assigned in a 1:1 ratio to either:

Confidential Page 10 of 33

- Single intranasal dose of OP0201 20 mg (4 sprays per nostril for a total of 8 sprays), or
- Single intranasal dose of placebo (4 sprays per nostril for a total of 8 sprays)

A fixed block size of 4 will be used. A sufficient number of extra randomization slots will be generated to allow for additional randomizations due to Study Participant discontinuations. The randomization scheme will be executed by an independent third-party vendor. Study treatment kit numbers will be assigned via Interactive Response Technology.

6.2 Blinding

Study treatment kits will be packaged and labeled by Catalent Pharma Solutions (Kansas City, MO, USA) in accordance with applicable national laws. Kits containing OP0201 or placebo will be identical in appearance. All clinical staff and Study Participants will be blinded to the assigned treatment.

6.3 Unblinding

If a serious AE (SAE) occurs during the study that meets the criteria for expedited reporting (i.e., is a Suspected Unexpected Serious Adverse Reaction), the Study Participant will be unblinded by Worldwide Clinical Trials pharmacovigilance. In an emergency situation, the investigator may unblind the Study Participant's treatment assignment.

7. ANALYSIS POPULATIONS

Screening Population: Study Participants who signed an Informed Consent Form and completed any screening procedures.

Randomized Population: Study Participants randomized prior to dosing. Study Participants will be summarized and analyzed per randomization assignment, regardless of treatment actually received.

Safety Population: Study Participants who received at least one spray of study treatment in either nare. Study Participants will be summarized and analyzed per treatment actually received, regardless of randomization assignment.

8. REPORTING AND ANALYSIS CONVENTIONS

8.1 Programming Environment

SAS® version 9.4 or higher (SAS Institute, Cary, North Carolina) will be used for statistical analyses and the production of tables, figures, and listings (TFLs).

8.2 Reporting Conventions

Tables of contents for TFLs to be produced are shown in Appendix B. TFLs will be appended to the final CSR. The following reporting conventions will be followed:

• Font size is to be no smaller than 9pt.

Confidential Page 11 of 33

- Titles and footnotes must appear on every page of the TFL.
- Treatment group names and order in tables and figures will be Placebo, OP0201 (20 mg). Some tables and figures may also display All Study Participants as a third grouping.
- Tables and figures will present summaries/analyses by study time point or analysis visit window, as appropriate.
- Table column headers and figure legends will include subgroup sample sizes ("N = xx"). Sample sizes reported as part of descriptive statistics ("n") will be the number of non-missing observations.
- Listings will be produced for all study population, safety, and efficacy data collected, either on the electronic case report form (eCRF) or through third-party vendors, and will be ordered by unique subject identifier, parameter, date, data collection time if applicable, nominal study visit, and analysis visit window if applicable (see Section 8.7).

8.3 General Analysis Conventions

Categorical variables will be summarized using frequencies and percentages. Percentages will be reported to one decimal place. Unless otherwise noted in Section 11, categorical variables will be analyzed using chi square tests of association or, if any contingency table cell has less than 5 subjects, Fisher's exact test.

Continuous variables will be summarized using descriptive statistics (e.g., n, mean, standard deviation, least-squares mean with standard error, distribution percentiles, range). The number of decimal places for minimums and maximums will be the same as the original data. The number of decimal places for means, medians, and interquartile ranges will be the same as the original data plus one. The number of decimal places for measures of variance will be the same as the original data plus two. Unless otherwise noted in Section 11, continuous variables will be analyzed using t-tests or a non-parametric alternative.

Data with qualifiers (e.g., "<") will be listed with but summarized without the qualifier.

P-values will be presented in summary tables to two decimal places if > 0.01, to three places if < 0.01 but > 0.001, and to four places if < 0.001 but > 0.0001. However, p-values > 0.045 but < 0.055 will also be presented to three decimal places. P-values < 0.0001 will be presented as "< 0.0001."

Statistical tests will be two-sided and tested at the 0.20, 0.10, and 0.05 significance levels in a hierarchical manner.

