5.2.5 Demographic and Baseline Characteristics

Demographics (sex, age, race, and ethnicity) and baseline characteristics (weight, height, and BMI) will be summarised using the appropriate descriptive statistics as described above for the Safety Population. No formal statistical analyses will be conducted. Data analyses will be provided by treatment and for all subjects combined (overall), where appropriate.

Baseline VAS, NRS-11, and otoscopy assessments will be summarised by treatment and overall (where applicable) using the appropriate descriptive statistics for all subjects in the Safety Analysis Population.

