11. SAFETY PARAMETERS

Safety parameters will be listed for the Randomized Population and summarized for the Safety Population unless otherwise noted.

11.1 **AEs**

AEs reported from time of first dose through EOS will be coded according to MedDRA® version 21.1 or later. Each reported AE will be mapped to a PT and SOC. Aside from parameters collected on the eCRF, listings will include date and time of study treatment dosing, MedDRA PT and SOC, Study Day, whether or not the AE is ongoing, AE duration, and whether or not the AE resulted in study discontinuation. For AEs that are ongoing, AE end date will be imputed with subject-level EOS date for the duration calculation.

A treatment-emergent AE (TEAE) will be defined as an AE that began or worsened during or after study treatment dosing on Day 1 and no later than on Day 2. AEs with insufficient date or time information to determine whether or not they were treatment-emergent will be considered treatment-emergent. AEs that began or worsened in severity from Day 3 through EOS will be defined as non-treatment-emergent. AEs that began or worsened in severity before first dose will be recorded as medical history.

All TEAEs will be listed. In addition, separate listings will be done for:

- Treatment-emergent SAEs (TESAEs), to include seriousness criteria
- TEAEs that resulted in study treatment interruption or dose reduction

Confidential Page 16 of 33

- TEAEs that results in discontinuation from the study or study treatment (excluding deaths)
- TEAEs that resulted in death
- Non-treatment-emergent AEs

Listings will be done for the Safety Population.

Incidence of all TEAEs will be summarized by SOC and PTs within SOCs, sorted alphabetically by SOC and PT within SOC unless otherwise noted. In addition, separate summaries will be done for:

- TEAEs assessed as related to study treatment
- TEAEs by maximum severity, with both SOCs and PTs within SOCs sorted by descending incidence among all Study Participants combined
- TESAEs
- TESAEs assessed as related to study treatment

In summaries by relationship to study treatment and maximum severity, missing relationship will be considered related and missing severity will be considered severe. Only the most related TEAE per subject for a given PT will be counted in summaries by relationship; similarly, only the most severe TEAE will be counted in summaries by severity.

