11.4 Vital Signs

Vital signs will be collected at Baseline and at 60 minutes post dose (or early termination). Observed values for oral temperature, respiratory rate, pulse, and systolic and diastolic blood pressure will be summarized at each time point. Changes from baseline will also be summarized for each post baseline time point. Listings will include changes from baseline.

Incidence of clinically meaningful changes from baseline to 60 minutes post dose will be summarized, with clinically meaningful changes defined as follows:

- Systolic BP: $\leq 80 \text{ mmHg or } \geq 140 \text{ mmHg}$
- Diastolic BP: supine $\leq 40 \text{ mmHg or } \geq 90 \text{ mmHg}$
- Pulse rate: ≤ 50 bpm or ≥ 100 bpm
- Respiration rate: < 8 or > 20 breaths per minute

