| Based on \geq 50 and 75% reduction | Response will be analyzed using general |
| | estimating equations (GEE). |
| CIs will be calculated using a fixed-effects | |
| model. | |
| PGIC and CGI-I will be analyzed using a | Site included as a random effect if doing so |
| mixed-effects model for repeated | appreciably affects treatment effect estimates. |
| measures with treatment group, visit, and site | |
| as factors and baseline score (PGIC and CGI- | Baseline NRS-11 will be used as a covariate. |
| I) as a covariate. | |
| Prior and concomitant medications will be | Summaries for prior medications will be |
| summarised using frequencies and | based on the Randomized Population. |
| percentages of subjects by treatment | Summaries for concomitant medications will |
| using the Safety Analysis Population. | be based on the Safety Population. |
| | |
| Only safety assessments with both predose | All safety data will be summarized. |
| and post-dose data will be analyzed. | - |
| For appearance of the TM, 80% CIs will be | Statistical inference for appearance of TM has |
| calculated for the incidence of shifts from | been removed. |
| Baseline (0-60 min), from normal to abnormal | |
| for the right ear and, separately, for the left | |
| ear. If significance is found using 80% CIs, | |
| 90% and 95% CIs will also be tested. | |
| Extent of exposure will be described by | Total exposure will be expressed as number |
| whether the subject took any study drug. | of sprays and will be summarized both per |
| | nostril and overall. |
| | Within-subject analyses will be done for PID |
| | and SPID. |
| | |

Confidential Page 26 of 33

REFERENCES

- 1. International Conference on Harmonisation of Technical Requirements for Registration of Pharmaceuticals for Human Use, ICH Harmonised Tripartite Guideline, Statistical Principles for Clinical Trials (E9), September 1998.
- 2. American Statistical Association (ASA). (2018) Ethical Guidelines for Statistical Practice. Prepared by the Committee on Professional Ethics, April 2018. http://www.amstat.org/ASA/Your-Career/Ethical-Guidelines-for-Statistical-Practice.aspx.
- 3. International Conference on Harmonisation of Technical Requirements for Registration of Pharmaceuticals for Human Use, ICH Harmonised Tripartite Guideline, Structure and Content of Clinical Study Reports (E3), November 1995.

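### SAP 8.3 takes its exceptions to the default tests from the wrong section: the rule collides with the plan's own no-test statements, leaves p-values on AE, ENT and vital-sign tables unclear, and Section 11 gives the primary endpoints no between-arm estimate

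*SAP*

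**What the plan says.** SAP 8.3 sets a default test for each type of variable. The first default is that "categorical variables will be analyzed using chi square tests of association or, if any contingency table cell has less than 5 subjects", Fisher's exact test. The second is that "continuous variables will be analyzed using t-tests or a non-parametric alternative". Both sentences carry the same single carve-out: anything noted otherwise in Section 11. The same section fixes the level: "Statistical tests will be two-sided and tested at the 0.20, 0.10, and 0.05 significance levels in a hierarchical manner". SAP 13.1.5 plans no multiplicity adjustment.

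Section 11 is Safety Parameters. It opens with "Safety parameters will be listed for the Randomized Population and summarized for the Safety Population unless otherwise noted" and continues in that vein. For AEs, "Incidence of all TEAEs will be summarized by SOC and PTs within SOCs"; for vital signs, "Changes from baseline will also be summarized for each post baseline time point". It names no test, no alternative to the default, and nowhere says that tests are omitted. The methods that do depart from the default (MMRM, GEE, GLM) and the explicit bars on inference are in Sections 12 and 13, which 8.3 does not except.

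Two other places speak directly against testing. Protocol 5.2.5 says of demographics and baseline characteristics: "No formal statistical analyses will be conducted". The change table in SAP 15 reads "Statistical inference for appearance of TM has" been removed.

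The primary objective (Protocol 2.1, SAP 2.1) is the safety of OP0201 20 mg relative to placebo. SAP 4.2.1 lists AEs, vital signs, ENT findings and TM appearance as the primary endpoints.

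**The concern.** A programmer who follows 8.3 as written would put p-values on tables that other parts of the plan say carry none. For the remaining safety tables the programmer could not tell either way. The protocol (5.2.6.1) defines p < 0.20 as significant for the exploratory analyses. Its one use of 80% limits on a safety endpoint, TM shifts (5.2.7.5), is what SAP 15 withdrew. Section 8.3 states the 0.20 level without that limit, so it can reach the primary safety endpoints.

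Such tests would mislead in both directions in a study this small. Vital-sign tests at 0.20 would throw up chance signals. AE comparisons would rarely reach significance and would invite the reading that the arms do not differ. What a comparative safety objective needs is a difference with its uncertainty, and Section 11 specifies none. The exploratory PID, SPID, response, PGIC and CGI-I results all receive between-arm differences with 80, 90 and 95% CIs (SAP 12.1.1, 12.1.2).

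**Working it through.** **1. The plan's own figure.** Protocol 5.2.1 gives about 24 subjects, 12 + 12 = 24. It gives no event rate, SD, effect size or power, so no power calculation can be reproduced. The steps below use n = 12 per arm.

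**2. The default rule set against the other text.**

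| Data | SAP 8.3, literally | Other text | Result |
|---|---|---|---|
| Demographics, baseline (SAP 9.5) | Tested | Protocol 5.2.5 excludes formal analysis; SAP 15 lists no change to this | Conflict |
| TM appearance (SAP 11.3) | Tested | SAP 15 removes inference | Conflict |
| Percent change, presence of pain, improvement category, time to relief (SAP 12.1.1) | Tested | 12.1.1 bars inference | Conflict |
| AOM symptoms (SAP 12.1.3) | Tested | 12.1.3 bars inference | Conflict |
| AEs, ENT findings, vital signs (SAP 11.1, 11.2, 11.4) | Tested | Listed and summarised only; nothing for or against a test | Unclear |

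Replacing Section 11 by Sections 12 and 13 in the carve-out resolves the two Section 12 rows. It does not resolve the others, because nothing in Sections 9 or 11 switches the default off.

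**3. If vital signs were tested at 0.20.** SAP 11.4 has five measures: temperature, respiratory rate, pulse, systolic and diastolic pressure. Assuming no true difference and independent tests, the chance of at least one p < 0.20 is 1 − 0.80^5 = 0.672. At 0.05 it is 1 − 0.95^5 = 0.226. Independence is an assumption; positive correlation lowers the first figure, to 0.20 if all five tests moved as one.

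**4. If AEs were tested.** For x/12 against 0/12, two-sided Fisher p = 2 × C(12,x) / C(24,x).
- x = 3: 2 × 220 / 2024 = 0.217
- x = 4: 2 × 495 / 10626 = 0.093

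So a 25-point imbalance is not significant even at 0.20. Power at 0.20, found by summing the binomial probabilities of all outcomes with p < 0.20, is 25% for assumed rates of 5% v 25% and 28% for 10% v 30%. The documents give no rates, so these are illustrations.

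**5. What an estimate would show instead.** For the same 3/12 v 0/12, using Newcombe's method:
- Wilson 95% limits are 0.089 to 0.532 for 3/12, and 0 to 0.242 for 0/12.
- Lower limit: 0.25 − √[(0.25 − 0.089)² + 0.242²] = −0.041.
- Upper limit: 0.25 + (0.532 − 0.25) = 0.532.
- Risk difference: 25 points, 95% CI −4.1 to 53.2.

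For a vital-sign change, the unadjusted 95% half-width is t(0.975, 22 df) × √(2/12) = 0.85 SD.

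**The case against.** The best case against is that safety was meant to be descriptive and 8.3 merely carries a stale cross-reference. Section 11 only lists and summarises. Section 12 names its models and intervals wherever inference is intended. The Appendix B safety tables are titled as incidences, observed values, changes and shifts, and Protocol 5.2.7.2 to 5.2.7.4 are descriptive. A careful reader would also let the specific statements in 12.1.1, 12.1.3 and SAP 15 prevail over a general convention. This is probably the intention, and it counts against two stronger readings:

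- A reader might infer that tests on every safety table are ruled out elsewhere. Express contrary text exists only for baseline data and TM appearance (and, outside safety, for the Section 12 items). For AEs, ENT findings and vital signs, testing is unaddressed.
- A reader might infer that the safety tables will carry p-values. That follows only from a literal reading of 8.3.

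The objection does not remove the defect. Where the authors wanted no inference in Section 12 they said so; Section 11 has no such sentence. For baseline data the specific prohibition is in the protocol, which Protocol 5.2 makes subordinate to the SAP where they differ, so precedence does not rescue it.

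SAP 13.1.2 might be offered as the missing estimate for vital signs, since its GLM for non-repeated continuous endpoints is worded generally. But Section 11.4 does not cite it, whereas 12.1.1 and 12.1.2 do cite Section 13. If it applies, it competes with the t-test in 8.3.

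It is also fair that per-arm summaries display the comparison descriptively, and that omitting intervals contradicts nothing in a 24-subject proof-of-concept study. Finally, the general limits of 12 per arm, such as an exact 95% upper limit of 26.5% for 0/12, hold whatever 8.3 says and are no evidence for this point.

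**Conclusion.** The point holds in limited form. The carve-out in SAP 8.3 names a section that contains no exceptions. Applied as written, the rule contradicts Protocol 5.2.5, SAP 15 and SAP 12.1.1 and 12.1.3. For AEs, ENT findings and vital signs it leaves open whether p-values appear, at a level the protocol reserves for exploratory work. Separately, Section 11 specifies no between-arm difference or interval for a primary objective framed against placebo. That is a weakness in meeting the objective, not a contradiction.

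The 67% figure assumes five independent tests that are actually run. The Fisher and risk-difference figures rest on illustrative counts and rates. No efficacy model is affected, but the wording should be settled before the tables are programmed.

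**What to change.** 1. In SAP 8.3, change the carve-out from Section 11 to Sections 12 and 13.
2. State in 8.3, or in Sections 9 and 11, that baseline, disposition and safety data are not hypothesis-tested.
3. Limit the 0.20 level to the exploratory analyses, and say that Section 13 serves the Section 12 endpoints.
4. Add to existing Appendix B tables: a risk difference with a score or exact-unconditional 95% CI for any TEAE and for related TEAEs (Table 14.3.1.1), and a between-arm mean difference with 95% CI for each vital-sign change (Table 14.3.9.1).
5. Treat any interval for TM shifts as optional, because SAP 15 deliberately removed that inference. If given, restrict it to ears that are normal at baseline on the feature concerned. Protocol 3.3.1 requires a bulging TM, so an affected ear cannot move from normal to abnormal contour, and fewer than 12 per arm may be at risk.

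The cost is SAP wording and extra table columns, with no new data or subjects. The downside is that the wide intervals at 12 per arm will make the safety statement look less favourable.

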8.4 Subgroups

There are no planned analyses by subgroups.

8.5 Missing Data

Listings will present data as reported. Missing or partially missing dates that are required for date-dependent definitions (e.g., treatment-emergent AEs, concomitant medications) will be assumed to be the most conservative date possible. For example, an AE with a completely

Confidential Page 12 of 33

missing start date will be considered treatment-emergent. Missing observations will not be imputed for summaries. Handling of missing observations for statistical inference is described in Section 13.1.4.

8.6 Study Period and Time Point Definitions

Screening: Day 1 up to dosing.

Baseline Observation: for a given parameter for a given randomized Study Participant, the last observed value before the first dose of study treatment or planned first dose of study treatment if not dosed.

Study Day 1: for a given randomized Study Participant, the day of actual first dose of study treatment or planned first dose of study treatment if not dosed.

Study Day:

- Study day = date of assessment date of dosing + 1, for assessments on or after first dose
- Study day = date of assessment date of dosing, for assessments before first dose

Study Time: time of assessment – time of first dose

Duration:

- Duration in days = end date start date + 1
- Duration in minutes = end time start time

(Nominal Visit) Analysis Time Point: analysis based on data collected at the (nominal visit) time point, where nominal visits are as shown below in Section 8.7.

End of Study (EOS), Study Participant-Level: the date of completion of the last planned study visit or date of discontinuation for any reason.

EOS, Study-Level: the date when all randomized Study Participants have reached Study Participant-Level EOS.

8.7 Visit Windows

Visit windows are based on Study Day and Study Time. Observations will be assigned to an analysis window according to the tables below. Observations that cannot be assigned to an analysis window based on the tables below will be excluded from summaries and analyses (but will still be listed). For Study Participants not dosed, planned date and time of first dose will be used in Study Day/Time calculations, if necessary.

For NRS-11, VAS, and PGIC on Study Day 1:

Confidential Page 13 of 33

| Nominal Visit | Min Study Time Per Protocol | Max Study Time Per Protocol | Min Study Time for Analyses | Max Study Time for Analyses |
|--------------------|-----------------------------------|-----------------------------------|-----------------------------------|-----------------------------------|
| Screening/Baseline | N/A | < 0 | N/A | < 0 |
| Day 1, Minute 10 | 10 | 10 | 0 | 14 |
| Day 1, Minute 20 | 20 | 20 | 15 | 24 |
| Day 1, Minute 30 | 30 | 30 | 25 | 44 |
| Day 1, Minute 60 | 60 | 60 | 45 | 75 |

N/A, not applicable

For all other assessments on Study Day 1:

| Nominal Time Point | Min Study Time Per Protocol | Max Study Time Per Protocol | Min Study Time for Analyses | Max Study Time for Analyses | |
|-----------------------|-----------------------------------|-----------------------------------|-----------------------------------|-----------------------------|--|
| Screening/Baseline | N/A | < 0 | N/A | < 0 | |
| Day 1, Minute 60 | 60 | 60 | 45 | 75 | |

N/A, not applicable

If multiple valid, non-missing observations exist within a given window, the observation to be used will be:

- 1. the observation closest to the nominal visit in question, or
- 2. the latest observation if the multiple observations are equidistant from the nominal visit, or
- 3. the average (arithmetic or geometric, as appropriate) of the observations if the multiple observations have the same actual time point.

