11.2 ENT Examination

ENT examination will be done at Baseline and 60 minutes post dose (or early termination). Findings are expressed as normal, abnormal not clinically significant, and abnormal clinically significant and will be summarized separately for ear, nose, and oropharynx at each time point. A shift table will summarize changes from baseline to 60 minutes post dose.

Confidential Page 17 of 33

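### The single 45–75 min window leaves early or late ENT, otoscopy and vital-sign exams out of the primary safety tables, although SAP Section 15 says all safety data are summarised

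*SAP*

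**What the plan says.** SAP Section 8.7 assigns observations by elapsed time, not by visit label: "Visit windows are based on Study Day and Study Time". Anything that fits no window is handled as follows: "Observations that cannot be assigned to an analysis window based on the tables below will be excluded from summaries and analyses". The same sentence adds that such values stay in the listings.

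Two window tables follow. One covers NRS-11, VAS and PGIC. The other is introduced by "For all other assessments on Study Day 1" and so governs ENT, otoscopy and vital signs. Its only post-dose row is "Day 1, Minute 60 | 60 | 60 | 45 | 75", where the last two figures are the analysis limits in minutes. Neither table has an early-termination row.

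Other parts of the plan treat the early-termination exam as a planned one:

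- SAP Section 11.2: "ENT examination will be done at Baseline and 60 minutes post dose (or early termination").
- SAP Section 11.4: "Vital signs will be collected at Baseline and at 60 minutes post dose (or early termination"). Section 11.3 has the same arrangement for otoscopy.
- SAP Appendix A and protocol Table 3.2 put minute 60 and early termination in one column. Protocol Section 3.5.3 requires all three exams from subjects who terminate early.
- SAP Section 15, in the changes table: "All safety data will be summarized". No exception is made for windows.

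SAP Section 4.2.1 lists four primary endpoints: adverse events, and change from baseline at 60 minutes in vital signs, ENT findings and tympanic membrane appearance.

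**The concern.** A programmer who follows Section 8.7 will leave an early-termination exam at, say, minute 20 out of the post-dose tables. A reader of Section 15 and the schedule will expect to find it there. No section says which should prevail.

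The exams concerned carry three of the four primary endpoints. Protocol Section 3.3.3 lists adverse events among the reasons for early termination, so a subject whose exam is left out may be one who reacted to the spray. The loss could then be informative, and would lower the abnormal rate in whichever arm it occurred. For the tympanic membrane, SAP Section 15 also removes the planned confidence intervals, so the descriptive tables are the whole summarised result.

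The two window tables are also uneven. A pain score from a subject who stops at minute 20 enters an exploratory table. A primary safety exam taken in the same minute does not enter a safety table.

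**Working it through.** There is no power or sample-size figure to reproduce. The check applies the Section 8.7 rule minute by minute and then sizes the result.

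**1. Where an exam lands, by whole minute of Study Time**

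| Study Time (min) | NRS-11, VAS, PGIC | ENT, otoscopy, vital signs |
|---|---|---|
| 0–14 | Minute 10 | no window: listed only |
| 15–24 | Minute 20 | no window: listed only |
| 25–44 | Minute 30 | no window: listed only |
| 45–75 | Minute 60 | Minute 60 |
| over 75 | no window: listed only | no window: listed only |

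Of the 60 whole minutes 0–59, in which a subject could stop before the minute-60 exam, 45 lead to exclusion of a safety exam (45/60 = 75%) and 15 to inclusion (15/60 = 25%). For the pain scores and PGIC, 0 of 60 lead to exclusion.

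**2. Weight of one subject**

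The planned arm size is 12 (protocol Section 5.2.1). One subject is 1/12 = 8.3%.

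**3. Effect of replacement**

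Protocol Section 3.3.3 and SAP Section 5 replace subjects who discontinue. SAP Section 7 keeps anyone who received at least one spray in the Safety Population. Assume two dosed subjects in one arm stop before minute 45, both have new abnormal findings, and both are replaced in that arm by unaffected subjects who complete.

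- All exams shown: 2/(12 + 2) = 2/14 = 14.3%.
- Section 8.7 as written: 0/12 = 0%.

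The evaluable count at minute 60 then equals the planned 12. Under SAP Section 8.2 the column header would show N = 14 against n = 12, so a careful reader could find the gap, but the table would not show what those two exams found.

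**4. Chance that it arises at all**

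The documents give no termination rate. Assume each of 24 subjects stops before minute 60 with probability r, uniformly in time, and is examined at once. From step 1 the probability of a dropped exam is 0.75r per subject, so P(at least one) = 1 − (1 − 0.75r)^24.

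| r | P(at least one dropped exam) |
|---|---|
| 1% | 16.5% |
| 2% | 30.4% |
| 5% | 60.0% |
| 10% | 84.6% |

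These figures ignore replacements. They fall if sites manage to bring early stoppers to the minute-60 exam, as protocol Section 3.3.3 asks.

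**The case against.** A reader might infer that the window removes early-termination exams altogether and so overrides sections that promise to use them. The documents do not support that.

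- Exams at 45–75 min are kept, and protocol Section 3.3.3 asks investigators to make every effort to complete the 60-minute or early-termination assessments.
- SAP Sections 11.2–11.4 say that the exams are done or collected. They do not say that an early one enters the 60-minute summary. The endpoints and shift tables are tied to 60 minutes, and a window around that time is consistent with them.
- The Section 15 sentence replaces the protocol's rule that only safety assessments with both pre-dose and post-dose data are analysed. It was not written about windows.

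A reader might also infer that the plan hides reactions. That is too strong. Excluded exams remain in by-subject listings, which can be read in full in a trial of about 24. Treatment-emergent adverse events are defined by onset or worsening, not by this window, and those leading to discontinuation are summarised and listed. Affected ears must enter with a bulging membrane, so their contour is already abnormal and cannot shift from normal to abnormal.

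All of this stands and limits the point. It does not close the gap. The Section 15 sentence is unqualified whatever it replaced, and the combined schedule column makes the early-termination exam a planned observation with no summary row. The contour argument does not reach the other membrane features, the unaffected ear, the observed-value tables, ENT findings or vital signs.

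The last objection concerns the remedy: labelling a minute-5 pulse as the minute-60 value would blur an endpoint defined at 60 minutes, and SAP Section 8.5 rules out imputation for summaries. That is right, and the change proposed here avoids it.

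**Conclusion.** The point holds in a limited form. As written, Section 8.7 keeps ENT, otoscopy and vital-sign exams taken before minute 45 or after minute 75 out of the summary, shift and change tables for three of the four primary endpoints. That does not fit the combined schedule time point or the unqualified sentence in Section 15.

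The size is about 8.3% of an arm per affected subject. The 2/14 against 0/12 comparison rests on an assumed pattern of stopping and replacement, and the probabilities on assumed rates. No bias for or against OP0201 can be claimed in advance, because nothing indicates in which arm early stops would fall.

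Severity is minor to moderate. No hypothesis test changes, no data are lost from the listings, and the adverse event tables are unaffected. It is still worth settling before unblinding, so that the display of a primary safety finding is not decided after it has been seen.

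**What to change.** In SAP Section 8.7, keep 45–75 min as the Minute 60 window. For ENT, otoscopy and vital signs, add one row covering post-dose exams outside that window, either as a flagged early-termination/out-of-window row or as a last-post-dose-value row. Carry it into the observed-value, shift and change tables, separate from Minute 60. Amend Sections 11.2–11.4 to say where an early-termination exam is displayed, and make Section 15 agree.

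If the sponsor intends such exams to be listed only, saying so and qualifying Section 15 would remove the contradiction. It would leave those findings out of the summary tables, so the extra row is preferable.

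The cost is one derivation or table row and some wording. A few displayed values will be off the nominal time, which the flag makes plain. The Minute 60 endpoint is unchanged.
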